7.1 Efficacy Assessments

Not applicable.

7.2 Safety Assessments

7.2.1 Laboratory Assessments

Clinical laboratory tests will be performed at a local laboratory (apart from drugs of abuse and alcohol tests performed at the clinical unit).

Blood samples will be collected via a peripherally placed intravenous cannula or by direct venipuncture in a suitable vein.

Blood samples for serology, hematology and biochemistry and urine samples for urinalysis will be collected as indicated in the Schedule of Assessments [Table 1] and Sample Collection Schedule [Table 2]. The clinical laboratory tests to be performed in the study are listed in [Section 10.6 Appendix 6 Clinical Laboratory Assessments].

Drugs of abuse and alcohol tests will be performed according to the clinical site's preferred method as indicated in the Schedule of Assessments [Table 1].

Pregnancy tests (female participants only) will be performed according to the clinical site's preferred method as indicated in the Schedule of Assessments [Table 1].

A blood sample will be collected for follicle-stimulating hormone (FSH) tests (postmenopausal female participants only) as indicated in the Schedule of Assessments [Table 1].

If any of the clinical laboratory tests results are outside the normal range at any scheduled time point during the study, an investigator may decide to repeat the test(s) on new samples. The clinical relevance of the abnormal results will be documented. Clinically relevant changes will be recorded as AEs (see [Section 7.3 Adverse Events and Other Safety Aspects]).

7.2.2 Vital Signs

Blood pressure (systolic and diastolic blood pressure), pulse, respiratory rate and oral temperature will be taken as indicated in the Schedule of Assessments [Table 1] and Sample Collection Schedule [Table 2]. Measurements will be taken after the participant has been resting in the supine position for at least 5 minutes. Measurements will be taken in duplicate with approximately 2-minute intervals at screening and on day -1 and at all other time points as single measurements.

7.2.3 Continuous Pulse Oximetry and Spot Blood Oxygen Saturation

Continuous pulse oximetry will be taken as indicated in the Schedule of Assessments [Table 1]. Continuous pulse oximetry will be measured using a pulse oximeter placed on the participant's fingertip. The alarm value will be < 90% for the continuous pulse oximetry, which may indicate opioid-induced respiratory depression.

Spot blood oxygen saturation (SpO₂) levels will be measured as indicated in the Schedule of Assessments [Table 1] and Sample Collection Schedule [Table 2]. SpO₂ will be measured using a pulse oximeter placed on the participant's fingertip.

7.2.4 Electrocardiogram

7.2.4.1 12-lead Electrocardiogram

12-lead ECGs will be taken as indicated in the Schedule of Assessments [Table 1] and Sample Collection Schedule [Table 2]. 12-lead ECGs will be taken after the participant has been resting in the supine position for at least 5 minutes. 12-lead ECGs will be taken in triplicate with approximately 1-minute intervals and all 3 ECGs will be completed within approximately 5 minutes.

The investigator will use the system at the phase 1 unit to review, sign and date the ECG after recording to ensure participant safety. The time of the ECG, the interval measurements, as well as an overall conclusion, will be documented. This overall conclusion will be recorded as normal, abnormal not clinically significant, or abnormal clinically significant. If the overall conclusion is abnormal, the applicable abnormality code as provided by the sponsor must be recorded. Considering their relatively rare occurrence in healthy participants, an ECG judged as abnormal clinically significant by an investigator for phase 1 studies must be further evaluated by another investigator, and if confirmed will be recorded as an AE.

Per time point, the ECG printouts will be reviewed in a timely manner by the investigator. Paper ECGs will be stored with the participant source. The time of the ECG, the interval measurements and the overall conclusion will be transcribed into the electronic CRF.

7.2.5 Physical Examination

Physical examination will be performed as indicated in the Schedule of Assessments [Table 1] and whenever there is a medical indication.

The investigator should examine the body systems as described in the clinical site's SOP for physical examination. New or worsening clinically significant physical examination findings after IP administration will be recorded as AEs if they meet the criteria in [Section 7.3 Adverse Events and Other Safety Aspects].

7.2.6 Columbia-Suicide Severity Rating Scale

The C-SSRS [Posner et al, 2009] is a feasible, low-burden rating scale that assesses the full spectrum of suicidality: suicidal ideation, intensity of ideation, suicidal behaviors and actual attempts. Ratings will be performed as indicated in the Schedule of Assessments [Table 1] using the C-SSRS [Section 10.8 Appendix 8 Columbia-Suicide Severity Rating Scale].

7.2.7 49-item Short Form of Addiction Research Center Inventory Scale

The 49-item short form of Addiction Research Center Inventory scale (ARCI-49) [Haertzen et al, 1963] is a standardized questionnaire for assessing subjective effects of psychoactive drugs and in discriminating some similarities and differences of naturally occurring and experimentally induced behavioral abnormalities. Participants will self-report using “sentence completion” and other association techniques. Only part 1 (i.e., 49-items) will be used. Ratings will be performed as indicated in the Schedule of Assessments [Table 1] and Sample Collection Schedule [Table 2] using the ARCI-49 [Section 10.9 Appendix 9 49-item Short Form of Addiction Research Center Inventory Scale].

7.2.8 Continuous and Spot End Tidal Carbon Dioxide

Continuous monitoring of end tidal CO₂ will be taken as indicated in the Schedule of Assessments [Table 1]. End tidal CO₂ measurements will be obtained by a health care professional directly monitoring a portable bedside capnography device. Time points for recorded measurements will be performed as indicated in the Schedule of Assessments [Table 1] and Sample Collection Schedule [Table 2]. The alarm values for the capnography continuous values, which may indicate potential respiratory depression, are high end tidal

CO₂, low respiratory rate and no breath alarms. Alarms during continuous end tidal CO₂ suggesting pulmonary issues other than opioid-induced respiratory depression include low end tidal CO₂ and high respiratory rate [see Table 5].

Table 5 Established Limits for End Tidal Carbon Dioxide

Parameter	Established Limit
End Tidal CO ₂ High	50 mmHg
End Tidal CO ₂ Low	25 mmHg
Respiratory Rate High	24 bpm
Respiratory Rate Low	6 bpm
No Breath Alarm	20 seconds

CO₂: carbon dioxide

7.2.9 Order of Assessments

All predose procedures, e.g., 12-lead ECG, vital signs and blood or urine sampling for clinical laboratory tests, will be performed within 60 minutes prior to dosing. All other measurements for 12-lead ECG and vital signs, will be performed within 15 minutes of the nominal time point. Pharmacokinetic sampling will be collected within 5 minutes from the nominal time point.

When time points for procedures overlap, blood sampling for pharmacokinetics will be collected at the nominal time point. Blood sampling for clinical laboratory tests, 12-lead ECG, vital signs (including SpO₂, if applicable), ARCI-49 and end tidal CO₂ are to be collected before or after the nominal blood sampling for pharmacokinetics.

7.3 Adverse Events and Other Safety Aspects

The definitions of an AE or SAE can be found in [Section 10.3.1 Appendix 3 Definition of Adverse Events and Section 10.3.3 Appendix 3 Definition of Serious Adverse Events], respectively.

AEs will be reported by the participant (or, when appropriate, by a caregiver, surrogate, or the participant's legally authorized representative).

The investigator and any qualified designees are responsible for detecting, documenting and recording events that meet the definition of an AE or SAE and remain responsible for following up AEs that are serious, considered related to the study IP, or that caused the participant to discontinue the IP and/or study [Section 10.3 Appendix 3 Adverse Events: Definitions and Procedures for Recording, Evaluating, Follow-up and Reporting].

The method of recording, evaluating, and assessing causality of AE and SAE and the procedures for completing and transmitting SAE reports are provided in [Section 10.3 Appendix 3: Adverse Events: Definitions and Procedures for Recording, Evaluating, Follow-up and Reporting].

7.3.1 Time Period and Frequency for Collecting Adverse Event and Serious Adverse Event Information

All SAEs will be collected from the signing of the ICF until the follow-up visit at the time points specified in the Schedule of Assessments [Table 1] and reported on the electronic data source.

All AEs will be collected from the signing of the ICF until the follow-up visit at the time points specified in the Schedule of Assessments [Table 1] and reported on the electronic data source.

If the severity of an AE/SAE changes, the event should be relisted on the electronic data source with the new severity and new onset date.

If the severity decreases, the AE/SAE should be relisted on the electronic data source with the new severity and new onset date. The exception is ongoing predose events that continue postdose and improve postdose. Such events should not be relisted.

If the severity of an SAE reduces, the details of the AE should be provided on the SAE worksheet for the medical assessor to be able to assess the course of the event.

All SAEs will be recorded and reported to the sponsor or designee immediately and under no circumstance should this exceed 24 hours, as indicated in [Section 10.3 Appendix 3: Adverse Events: Definitions and Procedures for Recording, Evaluating, Follow-up and Reporting]. The investigator will submit any updated SAE data to the sponsor within 24 hours of it being available.

Investigators are not obligated to actively seek AE or SAE after conclusion of the study participation. However, if the investigator learns of any SAE, including a death, at any time after a participant has been discharged from the study, and he/she considers the event to be reasonably related to the study IP or study participation, the investigator must promptly notify the sponsor.

7.3.2 Method of Detecting Adverse Events and Serious Adverse Events

Care will be taken not to introduce bias when detecting AEs and/or SAEs. Open-ended and nonleading verbal questioning of the participant is the preferred method to inquire about AE occurrences.

7.3.3 Follow-up of Adverse Events and Serious Adverse Events

After the initial AE/SAE report, the investigator is required to proactively follow each participant at subsequent visits/contacts. All SAEs and AEs of special interest (as defined in [Section 7.3.6 Adverse Events of Special Interest]) will be followed until resolution, stabilization, the event is otherwise explained, or the participant is lost to follow-up (as defined in [Section 8.3 Lost to Follow-up]). Further information on follow-up procedures is provided in [Section 10.3 Appendix 3: Adverse Events: Definitions and Procedures for Recording, Evaluating, Follow-up and Reporting].

If after the protocol-defined AE collection period (see [Section 7.3.1 Time Period and Frequency for Collecting Adverse Event and Serious Adverse Event Information]), an AE progresses to an SAE, or the investigator learns of any (S)AE (serious adverse event or adverse event) including death, where he/she considers there is reasonable possibility it is related to the IP or study participation, the investigator must promptly notify the sponsor.

7.3.4 Regulatory Reporting Requirements for Serious Adverse Events

- Prompt notification by the investigator to the sponsor of an SAE is essential so that legal obligations and ethical responsibilities towards the safety of participants and the safety of a study IP under clinical investigation are met.
- The sponsor has a legal responsibility to notify both the local regulatory authority and other regulatory agencies about the safety of a study IP under clinical investigation. The sponsor will comply with country-specific regulatory requirements relating to safety reporting to the regulatory authority, IRB/IEC and investigators.
- Investigator safety reports must be prepared for SUSAR according to local regulatory requirements and sponsor policy and forwarded to investigators as necessary.
- An investigator who receives an investigator safety report describing an SAE or other specific safety information (e.g., summary or listing of SAEs) from the sponsor will review and then file it along with the Investigator's Brochure and will notify the IRB/IEC, if appropriate according to local requirements.

7.3.5 Disease-related Events and/or Disease-related Outcomes Not Qualifying as Adverse Events or Serious Adverse Events

Not applicable.

7.3.6 Adverse Events of Special Interest

AEs of special interest are AEs the sponsor may wish to carefully monitor. These AEs may be serious or nonserious and should be reported on the electronic data source and the SAE worksheet. These AEs are not considered SAEs unless they meet the definition of an SAE.

AEs related to potential substance abuse and suicide (serious or nonserious) are considered to be of scientific and medical concern specific to ASP8062, for which ongoing monitoring and reporting is required.

Additional information around AEs of special interest will be collected to complete participant narratives. AEs of special interest related to potential substance abuse are listed in [Section 10.10 Appendix 10 Adverse Events of Interest Related to Potential Substance Abuse and Following Drug Withdrawal].

AEs of special interest with respect to morphine include respiratory depression, constipation, nausea, vomiting, sedation, somnolence, lightheadedness, dizziness, and sweating.

7.3.7 Special Situations

Certain special situations observed in association with the IP, such as incorrect administration (e.g., wrong dose of IP or background therapy) are reported as protocol deviations and/or

may require special reporting, as described below. These special situations are not considered AEs, but do require to be communicated to Astellas as per the timelines defined below.

If a special situation is associated with, or results in, an AE, the AE is to be assessed separately from the special situation and captured as an AE in the electronic data source. If the AE meets the definition of an SAE, the SAE is to be reported as described in [Section 10.3.7 Appendix 3 Reporting Procedures for Serious Adverse Events] and the details of the associated special situation are to be included in the clinical description on the special situation worksheet or pregnancy reporting form.

The special situations are:

- Pregnancy
- Lactation
- Medication error, overdose and “off-label use”
- Misuse/abuse
- Occupational exposure
- Suspected DDI

Instructions and procedures for reporting special situations are provided in [Section 10.3.8 Appendix 3 Reporting Procedures for Special Situations].

7.4 Pharmacokinetics

7.4.1 Analysis of ASP8062 and Metabolites in Plasma

Blood samples for the determination of ASP8062 and its metabolites (AS3486189, AS3486191 and AS3486192) in plasma will be collected as indicated in the Schedule of Assessments [Table 1] and Sample Collection Schedule [Table 2] for the evaluation of pharmacokinetics. If needed, other metabolites may also be measured.

Blood will be drawn in plastic tubes containing K₂-EDTA. The actual date and time of each blood sample collection will be documented. Plasma will be prepared according to procedures further specified in the laboratory manual. Samples will be shipped to the designated CRO and analyzed using a validated method.

When deemed appropriate at a later date, plasma samples remaining after the pharmacokinetic analysis may be used for exploratory metabolite profiling or exploratory biomarker analysis after the study. These tests will be described in a separate report and will not be incorporated in the integrated clinical study report (CSR).

7.4.2 Analysis of Morphine and Metabolites in Plasma

Blood samples for the determination of morphine and its metabolites (morphine-3β-D-glucuronide [M3G] and morphine-6β-D-glucuronide [M6G]) in plasma will be collected as indicated in the Schedule of Assessments [Table 1] and Sample Collection Schedule [Table 2] for the evaluation of pharmacokinetics. Plasma will be prepared

according to procedures further specified in the laboratory manual. Samples will be shipped to the designated CRO and analyzed using a validated method.

When deemed appropriate at a later date, plasma samples remaining after the pharmacokinetic analysis may be used for exploratory metabolite profiling or exploratory biomarker analysis after the study. These tests will be described in a separate report and will not be incorporated in the integrated CSR.

7.5 Pharmacodynamics

Not applicable.

7.6 Pharmacogenomics

Pharmacogenomic (PGx) research may be conducted in the future to analyze or determine genes of relevance to clinical response, pharmacokinetics, toxicity/safety. A 4 mL sample of whole blood for possible banked PGx analysis will be collected as indicated in the Schedule of Assessments [Table 1]. Samples will be shipped to a sponsor-designated sample banking CRO.

Details on sample collection, labeling, storage and shipment procedures will be provided in a separate laboratory manual.

See [Section 10.7 Appendix 7: Pharmacogenomic Analysis with Banked Sample] for further details on the banking procedures.

7.7 Biomarkers

Knowledge of polymorphisms of genes GABA_B receptors and/or opioid receptors may help understand/explain observed differences in efficacy/safety of ASP8062. A 2 mL whole blood sample for the analysis of these biomarker (genes) will be collected as indicated in the Schedule of Assessments [Table 1].

For detailed sample collection, sample labeling and sample shipment procedures refer to the laboratory manual. All samples will be transferred to the central laboratory and then shipped to the analytical laboratory where they will be analyzed using appropriate validated methods.

7.8 Immunogenicity Assessments

Not applicable.

7.9 Clinical Outcome Assessment

Not applicable.

7.10 Total Amount of Blood

The approximate total blood volume taken per participant will be as follows:

Table 6 Blood Volume

Sample Type	Number of Samples	Sample Volume (mL)	Total Volume (mL)
Clinical Laboratory Tests	16	9 (+ 8.5)†‡	152.5
ASP8062 and its Metabolites (Including AS3486189, AS3486191 and AS3486192) Pharmacokinetics	35	2.0	70.0
Morphine and its Metabolites (M3G and M6G) Pharmacokinetics	14	1.0	14.0
Biomarker Analysis	1	2.0	2.0
PGx Analysis	1	4.0	4.0
Total			242.5

M3G: morphine-3β-D-glucuronide; M6G: morphine-6β-D-glucuronide; PGx: pharmacogenomic

† Includes pregnancy test (female participants only) and follicle-stimulating hormone test (postmenopausal female participants only) at screening.

‡ Includes serology test at screening.

Additional blood may be drawn for safety reasons. The maximum amount of blood drawn during the study will not exceed 500 mL.

8 PARTICIPANT DISCONTINUATION

Refer to [Section 10.1.9 Appendix 1 Study and Site Start and Closure] regarding discontinuation of study sites or of the study as a whole.

8.1 Discontinuation of Individual Participant(s) from Study Treatment

A discontinuation from treatment is defined as a participant who enrolled in the study and for whom study treatment is permanently discontinued for any reason.

The participant is free to withdraw from the study treatment and/or study for any reason and at any time without giving reason for doing so and without penalty or prejudice. The investigator is also free to discontinue the participant from study treatment or to terminate a participant's involvement in the study at any time if the participant's clinical condition warrants it.

The reason for discontinuation from study treatment must be documented in the participant's medical records.

A participant must discontinue study treatment for any of the following reasons:

- Participant requests to stop treatment
- Any clinical AE, laboratory abnormality or intercurrent illness, in the opinion of the investigator, indicates continued treatment is not in the best interest of the participant

- Female participant becomes pregnant
- If participant experiences symptomatic decrease in SpO₂ requiring medical intervention prior to day 10 (predose)

8.2 Discontinuation of Individual Participant(s) from Study

All participants who discontinue study treatment will remain in the study and must continue to be followed for protocol-specific follow-up procedures as outlined in the Schedule of Assessments [Table 1]. The only exception to this is when the participant specifically withdraws consent for any further contact with him/her or persons previously authorized by the participant to provide this information.

8.3 Lost to Follow-up

Every reasonable effort is to be made to contact any participant lost to follow-up during the course of the study to complete study-related assessments, record outstanding data and retrieve IP. These contact attempts should be documented in the participant's medical record.

8.4 Discontinuation of the Study

The sponsor will terminate this study if 1 of the following criteria are met. The sponsor will unblind the affected participant(s) to an investigator/delegate before a final decision is made.

1. If after coadministration of morphine and ASP8062 or placebo on day 10, ≥ 5 ASP8062-treated participants experience ASP8062-related AEs of severe intensity that are considered by an investigator to be of clinical concern
2. If after coadministration of morphine and ASP8062 or placebo on day 10, ≥ 3 ASP8062-treated participants experience an ASP8062-related SAE and there is no plausible alternate explanation for these events
3. If after coadministration of morphine and ASP8062 or placebo on day 10, ≥ 5 ASP8062-treated participants show at least 1 of the following findings in 2 consecutive measurements within 24 hours postdose:
 - ALT or AST $\geq 3 \times$ ULN and ALT or AST is $> 3 \times$ day 9 (day prior to ASP8062 or placebo ASP8062 and morphine coadministration) values
 - ALT or AST $\geq 2 \times$ ULN and ALT or AST $\geq 5 \times$ day 9 (day prior to ASP8062 or placebo and morphine coadministration) values
 - TBL $\geq 2 \times$ ULN and participant does not have Gilbert Syndrome
4. If after coadministration of ASP8062 or placebo and morphine on day 10, ≥ 3 ASP8062-treated participants have QTcF interval > 500 msec in 2 consecutive measurements within 24 hours postdose
5. If after coadministration of ASP8062 or placebo and morphine on day 10:
 - ≥ 4 ASP8062-treated participants experience ASP8062-related symptomatic decrease in SpO₂ requiring more than 2 liters of supplemental oxygen via nasal cannula or,
 - ≥ 1 ASP8062-treated participant experiences ASP8062-related symptomatic decrease in SpO₂ requiring intubation, for medically significant respiratory depression.

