	8 hours	X	X	X			X	X	X
	12 hours	X	X	X		X	X		X
	16 hours	X	X						
11	24 hours postdose day 10	X	X	X	X		X		
	36 hours postdose day 10	X	X						
12	48 hours postdose day 10	X	X	X	X				
	60 hours postdose day 10	X							
13	72 hours postdose day 10	X		X	X				
14	96 hours postdose day 10	X		X	X				
15	120 hours postdose day 10	X		X	X				
16	144 hours postdose day 10	X		X	X	X			
ESV	5 to 9 days after the day 16 pharmacokinetic sample/ED/ET	X		X	X	X			

ARCI-49: 49-item short form of Addiction Research Center Inventory scale; CO₂: carbon dioxide; ECG: electrocardiogram; ED: early discontinuation; ESV: end-of-study visit; ET: early termination; SpO₂: blood oxygen saturation

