This will be the first study where a multiple daily oral dose of ASP8062 is administered in participants that will also be given morphine after the participants have reached near steady-state peak to trough exposures of ASP8062. Risks are minimized by confining participants in an experienced clinical unit testing the effects of approved medications or new chemical entities when combined with morphine. This study is also being conducted after the initiation of the phase 1b study examining a single dose of ASP8062 (60 mg) in participants also administered buprenorphine-naloxone at doses/exposures consistent with OUD standard of care. Continuous pulse oximetry and capnography for at least 8 hours will be employed on day 10 when ASP8062 is given with morphine so that the potential for respiratory depression will be noted immediately, and appropriate medical treatment may be given. Participants will also be monitored by experienced staff for signs of opioid withdrawal. Vital signs will be monitored daily from days 9 to 16 and electrocardiograms (ECGs) will be monitored on day 10 to detect potential cardiovascular symptoms several hours postdose. AEs will be assessed daily throughout the study. Potential hepatic toxicity will be monitored with clinical laboratory testing on at least a daily basis from days 10 to 16 of the investigational period.

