4.2 Scientific Rationale for Study Design

A randomized, participant- and investigator-blinded, placebo-controlled, single sequence study was chosen to assess the safety and tolerability of multiple doses of ASP8062 alone and ASP8062 in combination with a single dose of morphine sulfate, a full μ -opioid receptor agonist. Participants will be randomized to treatment to reduce selection bias. Participants and the investigator will both be blinded to treatment to reduce bias in the measurement of the primary safety endpoints. Given the long pharmacokinetic $t_{1/2}$ of ASP8062 (approximately 60 hours), a single sequence study was chosen.

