6.8 Concomitant Therapy

All medicinal products, including prescribed and nonprescribed drugs used prior to IP administration will be considered previous medication.

Specific restrictions on previous medications are provided in [Section 5.2 Exclusion Criteria].

All medication taken within 4 weeks prior to admission to the clinical unit will be documented.

All medicinal products other than the IP(s), including prescribed or nonprescribed drugs (including vitamins and natural and herbal remedies, e.g., St. John's Wort), used from first IP administration until the ESV will be considered concomitant medication.

Participants will only be allowed to use the following concomitant medication, if needed, from first IP administration until the ESV:

- Acetaminophen (up to 2 g/day)
- Topical dermatological products, including corticosteroid products
- Hormonal contraceptives
- HRT

If a participant's health condition necessitates the use of any medication other than the permitted medications during the study, an investigator and medical monitor, or designee(s), will discuss the case and determine if the participant should be withdrawn from the study and/or excluded from analysis sets, depending on if, and how, the medication(s) used influence(s) the study outcome. The nonpermitted concomitant medication will be recorded as a protocol deviation.

All concomitant treatments (medication and nonmedication therapy) will be documented.

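### On scheduled labs, liver stopping criterion 3 can be met only by the 2 h and 24 h samples after the day 10 dose, so a confirmed rise first seen at 24 h or later cannot trigger it

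*Combined protocol and SAP*

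**What the plan says.** Section 8.4, criterion 3, applies after the day 10 dose of morphine with ASP8062 or placebo. It requires the sponsor to stop the study when at least 5 ASP8062-treated participants "show at least 1 of the following findings in 2 consecutive measurements within 24 hours postdose". The findings are ALT or AST at least 3 × ULN and more than 3 times the day 9 value; ALT or AST at least 2 × ULN and at least 5 times the day 9 value; or total bilirubin at least 2 × ULN without Gilbert syndrome.

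Table 2 (Section 1.3) places one clinical laboratory draw at 2 h after the day 10 dose. The next is at "24 hours postdose day 10", and daily draws follow until "144 hours postdose day 10". Section 2.3.1 gives these labs a safety purpose: "Potential hepatic toxicity will be monitored with clinical laboratory testing on at least a daily basis from days 10 to 16". Section 7.2.1 adds that when a result is abnormal "an investigator may decide to repeat the test(s) on new samples", which is optional. Appendix 4 asks for a repeat within 72 hours of notification when aminotransferases exceed 3 × ULN or bilirubin exceeds 2 × ULN.

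**The concern.** The plan collects liver tests for six days after coadministration, but its only study-level laboratory rule for the liver reads the first day alone. Within that day, two scheduled samples must both be abnormal, and the first comes 2 h after dosing. For ALT/AST, the required multiple of the day 9 value must also have been reached by then. A rise first seen at 24 h and confirmed at 48 h has the confirmation that the rule asks for, but too late to count.

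At stake is an automatic halt. If several participants showed confirmed but asymptomatic rises on days 11 to 16, nothing in Section 8.4 would oblige the sponsor to stop dosing the remaining participants.

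**Working it through.** **Checking the reading of Table 2.** Lab draws: screening; day -1; day 1, day 3 and day 6 predose; day 9 predose and 2 h; day 10 predose and 2 h; then 24, 48, 72, 96, 120 and 144 h; and the end-of-study visit. That is 16, the number in Table 6. The volume also agrees: 16 × 9 + 8.5 = 152.5 mL.

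**Counting qualifying samples and pairs.** In-house labs after the day 10 dose fall at 2, 24, 48, 72, 96, 120 and 144 h, which is 7. Those later than 24 h number 5. Consecutive pairs that end inside the window:

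| Window after day 10 dose | Pairs |
|---|---|
| 24 h (current) | 1 (2–24) |
| 48 h | 2 |
| 72 h | 3 |
| 144 h | 6 (2–24, 24–48, 48–72, 72–96, 96–120, 120–144) |

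The single current pair depends on nominal time. Section 7.2.9 gives tolerances for post-dose ECGs, vital signs and PK samples, but none for post-dose safety labs. If actual time governed and the 24 h sample were drawn slightly late, no scheduled pair would remain.

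**Which rises can be confirmed.** A rise first seen at 2 h can be confirmed at 24 h. One found on an optional repeat between 2 h and 24 h can also be confirmed at 24 h. One first seen at 24 h is next sampled at 48 h, outside the window, and any repeat prompted by it is also too late. Every later rise fails in the same way.

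**Chance of meeting the rule.** The ASP8062 arm is 24 × 2/3 = 16; with 18 completers in the same ratio it is 18 × 2/3 = 12. Let p be the proportion with a confirmed rise first seen at 24 to 120 h, with participants independent. Then P(X ≥ 5) = Σ from k = 5 to n of C(n,k) p^k (1 − p)^(n−k). Every p is an assumption, because the documents give no rate.

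| Assumed p | Now | Window to 144 h, n = 16 | Window to 144 h, n = 12 |
|---|---|---|---|
| 10% | 0 | 1.7% | 0.4% |
| 15% | 0 | 7.9% | 2.4% |
| 20% | 0 | 20% | 7.3% |
| 30% | 0 | 55% | 28% |
| 40% | 0 | 83% | 56% |
| 50% | 0 | 96% | 81% |

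At 5% with n = 16 the probability is below 0.1%. The upper limit of 120 h applies because a rise first seen at 144 h has no later in-house lab; the next scheduled one is at the end-of-study visit, 5 to 9 days on. The table counts all participants, so it shows whether the rule would ever be met, not whether it would be met in time to spare anyone a dose.

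**Exposure after 24 h.** Section 4.2 puts the ASP8062 half-life at about 60 hours. On simple exponential decline, 2^(−24/60) = 76% of the starting level remains at 24 h and 2^(−144/60) = 19% at 144 h. Exposure therefore outlasts the window, though this alone does not show that new injury is expected then.

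**The case against.** The narrow window can be defended. Day 10 is the last ASP8062 dose, given near steady state, so concentrations fall afterwards. Labs on days 3, 6 and 9 already watch the liver during ASP8062 dosing, and the comparison with day 9 aims criterion 3 at the added effect of coadministration. Section 4.3 expects these exposures to be safe, from 137 healthy participants and 95 patients. At true rates of 10% to 15%, the 5-participant threshold limits the rule more than the window does. A stop after day 10 also cannot help those who trigger it.

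The backstops are substantial. Criteria 1 and 2 carry no time window. Potential Hy's Law cases are reported as SAEs (Section 10.3.2.1) and, if related to ASP8062 "and there is no plausible alternate explanation for these events", count toward criterion 2 at 3 participants. Appendix 4 treats ALT/AST above 3 × ULN with nausea, vomiting or fatigue as severe; such cases may be reported as SAEs, and the sponsor is informed if they are possibly attributable to study drug. Urgent safety measures (Sections 10.3.10 and 10.3.11) and sponsor discretion (Section 10.1.9) allow a halt at any time.

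All of this stands, and it limits the severity. It does not close the gap. Criterion 1 needs severe related AEs, and Section 10.3.5 defines severe as inability to perform daily activities, which an asymptomatic enzyme rise would not ordinarily meet. Isolated rises need not be SAEs. The remaining routes are individual or discretionary.

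A reader might infer that the rule cannot operate, or that late liver injury would go undetected. The documents support neither. The 2 h/24 h pair, or a repeat before 24 h, can meet the rule, and later rises are still measured and followed. They are missed by criterion 3 only. The phrase might also be read as two measurements within 24 hours of each other, but the text ties the window to the dose.

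**Conclusion.** The concern holds as a mismatch between one stopping criterion and the sampling schedule. The counts are certain: 1 qualifying scheduled pair, and 5 of 7 in-house post-dose labs unable to count. What no mandatory stop covers is 5 or more ASP8062 participants with confirmed ALT/AST or bilirubin rises first seen on days 11 to 16 that are neither severe related AEs nor related SAEs.

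The size of the benefit is not known. It is small at assumed rates of 10% to 15% and large only at 30% or more. It would tempt a reader to take 55% to 96% as the protection gained, but those figures need high assumed rates and a first rise between 24 and 120 h. The stop protects only participants not yet fully dosed. The documents describe no cohorts or staggering, so that number cannot be stated. This is a cheap improvement of modest severity.

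**What to change.** In criterion 3, replace the 24-hour limit with: *from the day 10 dose through day 16 (144 hours postdose, by nominal time), counting scheduled or repeat measurements, and including a repeat test that confirms a rise first seen on day 16*. This also settles whether the nominal 24 h sample counts.

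Criterion 3 has no relatedness test, and Section 6.8 permits acetaminophen up to 2 g a day, so the sponsor may want an alternate-explanation condition for pairs completed after 24 h. If so, state that the coadministered morphine is not an alternate explanation. Everyone receives it and Section 2.3.1 lists hepatitis among opioid side effects, so it could otherwise be cited for every late rise and cancel the change.

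Leave criterion 4 (QTcF) unchanged: ECGs at 2, 4 and 12 h fit its 24-hour window.

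The cost is one amended sentence with IRB/IEC approval, and no new scheduled samples or visits. A rise first seen on day 16 may need a retest after discharge, which Appendix 4 already asks for above its limits. The downside is a higher chance of stopping for unrelated rises: before any added condition, with 16 on ASP8062, below 0.1% at an assumed unrelated rate of 5%, 1.7% at 10%, 7.9% at 15% and 20% at 20%. An alternate-explanation condition would lower these chances and those for true effects. The unblinding step already in Section 8.4 gives a further check before a final decision.
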